#### 9.5 RULES FOR AMENDING PROTOCOL

All amendments must be documented, dated and signed by all signatories (or their successors) of the original protocol and then will be submitted to Regulatory Authorities/IEC/IRB. Modification only for logistical or administrative changes may be implemented immediately; however, both the IEC/IRB and the Regulatory Authorities will be notified immediately.

### 9.6 FINANCIAL DISCLOSURE

The PI and sub-investigators are required to provide financial disclosure information to the Sponsor to permit the Sponsor to fulfil their obligations. In addition, the PI/sub-investigator must commit to promptly update this information if any relevant changes occur during the study and for a period of 1 year after the completion of the study.

Protocol No.: SARO.17.010

CONFIDENTIAL
PAGE 72 OF 80

#### 9.8 FINAL REPORT AND PUBLICATION POLICY

A report will be prepared by the Sponsor. It will include the tabulated raw data and the biostatistical report on the data.

Zydus Discovery DMCC is, as much as possible, dedicated to support the process of free exchange of relevant scientific information. Any publication of the results of this study must be consistent with the ZYDUS publication policy. The rights of the PI and of the Sponsor with regard to publication of the results of this study are described in the Investigator agreement.

#### 9.9 ARCHIVING

Subject's files, identification codes and other source data (including original reports of test results, dispensing logs and records of informed consent), IEC/IRB approval letter, correspondence and other documents pertaining to the conduct of the study will be kept as per the SOPs of the institution. No document pertinent to the study shall be destroyed without prior written agreement between the Sponsor and the PI. All documents should be preserved safely after the completion/termination of the study for at least a period of 5 years if it is not possible to maintain the same permanently.

Approved by: [name] [name] Protocol No.: SARO.17.010

CONFIDENTIAL
PAGE 73 OF 80

### 11 APPENDICES

### Appendix 1: List of Known CYP2C8 Inhibitors/Substrates

Selected inducers, inhibitors and substrates of CYP2C8				
Substrates	Inhibitors	Inducers		
amodiaquine a (antimalarial, anti- inflammatory)     cerivastatin a (statin)     enzalutamide (antiandrogen)     paclitaxel a (chemotherapeutic)     repaglinide a (antidiabetic)     torasemide a (loop diuretic)     sorafenib a (tyrosine kinase	Strong  • gemfibrozila (hypolipidemic)  Moderate  • trimethoprima (antibiotic)  Unspecified potency  • thiazolidinedionesa (antidiabetic)  • montelukasta (leukotriene receptor antagonist)  • quercetina (antiinflammatory)	Unspecified potency  • rifampicin a (antibiotic)		

a Flockhart DA (2007). "Drug Interactions: Cytochrome P450 Drug Interaction Table". Indiana University School of Medicine. Retrieved on July 2011

### Appendix 2: NATIONAL INSTITUTES OF HEALTH- Diet History Questionnaire

(https://epi.grants.cancer.gov/dhq2/forms/)

Approved by: Protocol No.: SARO.17.010
[name] [name] Version No.: 7.0

b Chapter 26 in: Rod Flower; Humphrey P. Rang; Maureen M. Dale; Ritter, James M. (2007). Rang & Dale's pharmacology. Edinburgh: Churchill Livingstone. ISBN 0-443-06911-5

[figure not shown]

## 1. INTRODUCTION

The purpose of this document is to provide a description of the statistical methods and procedures to be implemented for the analysis of data from SARO.17.010 study. This document is based on protocol version 7.0, dated 01 Aug 2019. The statistical planning and conduct of analysis of the data from this study will follow the principles defined in relevant International Council for Harmonisation (ICH)-E9 guidelines. This Statistical Analysis Plan (SAP) has been developed prior to database lock and interim or final analysis. Any changes from the planned analysis as described in the protocol are detailed here, and any differences described here supersede the analysis as presented in the protocol. Any deviations from the planned analyses described in this SAP will be documented in the clinical study report, together with the reason for such changes.

Prior to start of any statistical analyses, the database must be authorized and all decisions regarding assignment of patients to study populations must be completed. In addition, protocol deviations must be identified prior to the start of statistical analyses.

## 2. STUDY OBJECTIVES AND DESIGN

### 2.1 Study Objectives

The objectives of this study are to evaluate the safety, tolerability and efficacy of Saroglitzazar magnesium in liver transplant recipients with nonalcoholic fatty liver disease (NAFLD) as assessed by Controlled Attenuation Parameter (CAP) and magnetic resonance imaging (MRI). Efficacy will be evaluated as a secondary objective.

#### Primary Objective

The primary objective of this study is to assess the safety of Saroglitzazar magnesium 4 mg in liver transplant recipients with non-alcoholic fatty liver disease (NAFLD) over 24 weeks of treatment.

#### Secondary Objectives

The secondary objectives of this study are to assess:

Statistical Analysis Plan			
Version Number:	1.0	Date:	31 Dec 2021
Protocol Number:	SARO.17.010	Sponsor Name:	Zydus Therapeutics Inc.

- Changes in hepatic fat as determined by magnetic resonance imaging-proton density fat fraction (MRI-PDFF) and magnetic resonance elastography (MRE) from baseline to end of treatment (EOT)
- Changes in metabolic flexibility from baseline to EOT
- Changes in markers of insulin resistance [frequently sampled intravenous glucose tolerance test (FSIVGTT), glycosylated hemoglobin (HbA1c) and fructosamine] from baseline to EOT
- Changes in serum liver enzymes from baseline to EOT
- Changes in serum lipids from baseline to EOT
- Changes in atherogenic lipoprotein which including small dense low-density lipoprotein (sdLDL), LDL size and concentration, subtypes of very low-density lipoprotein (VLDL), high-density lipoprotein (HDL) from baseline to EOT
- Change in Quality-of-life score from baseline to EOT using SF-36 health survey
- Pharmacokinetics of Saroglitzazar following first dose and last dose
- Body composition assessment via change in adipose tissue and skeletal muscle volume from baseline to EOT by whole body MRI.

## 2.2 Study Description

### 2.2.1 Study design

[figure not shown]
This is a Phase 2A prospective, single-center, open-label, single-arm study to evaluate the safety, tolerability and efficacy of Saroglitzazar magnesium 4 mg in liver transplant recipients with non-alcoholic fatty liver disease. Patients who are at least 6 months post-transplant for non-alcoholic steatohepatitis (NASH) or cryptogenic cirrhosis thought to be secondary to NASH are eligible to be enrolled in this study. Approximately 15 male and female patients aged 18 to 75 years who meet the inclusion and exclusion criteria will be enrolled. All eligible patients will receive Saroglitzazar magnesium 4 mg once daily in the morning for a period of 24 weeks.

This study will be conducted over a period of up to 33 weeks and will include a 5-week screening period, a 24-week treatment period and a safety follow-up visit, 4 weeks after the last treatment. The screening period may be extended under special circumstances with the explicit approval of the Sponsors' Medical Expert(s). The study visits will occur at Screening, Baseline (day 1), Week 4 (Day 29 ± 3 days), Week 8 (Day 57 ± 3 days), Week 12 (Day 85 ± 3 days), Week 16 (Day 113 ± 3 days), Week 20 (Day 141 ± 3 days) and Week 24 (Day 169 ± 3 days). A

Document Title:	Statistical Analysis Plan		
Version Number:	1.0	Date:	31 Dec 2021
Protocol Number:	SARO.17.010	Sponsor Name:	Zydus Therapeutics Inc.

[figure not shown]
safety follow-up visit will be conducted approximately 4 weeks after the administration of last dose of the study drug (Day 197 ± 3 days).

Approximately 5 patients will be included in the pharmacokinetic assessment. Pharmacokinetics of Saroglitzazar will be assessed following administration of first (Baseline) and last dose (Week 24). The samples will be collected at Pre-dose (0.0) and 0.5, 1.0, 2.0, 3.0, 4.0, 6.0, 8.0, 10.0 and 24 hours post-dose. In addition, pre-dose sample will be collected at Week 4, 8, 12, 16 and 20 Visits. The study plan is provided below.

Document Title:	Statistical Analysis Plan		
Version Number:	1.0	Date:	31 Dec 2021
Protocol Number:	SARO.17.010	Sponsor Name:	Zydus Therapeutics Inc.

## 2.2.2 Study plan

Document Title:	Statistical Analysis Plan		
Version Number:	1.0	Date:	31 Dec 2021
Protocol Number:	SARO.17.010	Sponsor Name:	Zydus Therapeutics Inc.

Document Title:	Statistical Analysis Plan		
Version Number:	1.0	Date:	31 Dec 2021
Protocol Number:	SARO.17.010	Sponsor Name:	Zydus Therapeutics Inc.

## 2.3 Randomization

Not applicable. This is an open-label single-arm study and all eligible patients will receive Saroglitzaz magnesium 4 mg treatment.

## 2.4 Blinding and Unblinding

The study is an open-label single-arm study. The study participants and the investigator will be aware about the study drug (Saroglitzaz magnesium 4 mg), is to be administered.

## 2.5 Interim Analysis

No interim analysis is planned for this study.

# 3. ANALYSIS POPULATIONS

Patient evaluability and their impact on analysis populations will be determined prior to locking the database.

## 3.1 Efficacy Analysis Populations

The modified intent-to-treat (mITT) population includes all enrolled patients who receive at least one dose of study drug and have at least one post-baseline assessment visit. The mITT population will serve as the primary analysis population for all efficacy analyses. Last observation carried forward (LOCF) method will be used as an imputation method for the efficacy variables with missing observations.

The supportive analysis of the efficacy endpoints will be conducted using per-protocol (PP) population. The PP population includes all enrolled patients who receive at least one dose of study drug, complete the study (Week 24 assessment) in compliance with the protocol and do not have any major protocol violations.

The number of patients excluded from mITT and PP populations and a listing of excluded patients from each analysis population with reason for exclusion will be presented.

## 3.2 Safety Analysis Population

The safety population includes all enrolled patients who receive at least one dose of study drug.

Document Title:	Statistical Analysis Plan		
Version Number:	1.0	Date:	31 Dec 2021
Protocol Number:	SARO.17.010	Sponsor Name:	Zydus Therapeutics Inc.

### 3.3 Pharmacokinetic Analysis Population

The pharmacokinetic population includes all enrolled patients with evaluable concentration profile and do not have any major protocol deviation(s) that could affect the PK profile of the study drug.

## 4. SAMPLE SIZE AND POWER CALCULATIONS

Due to exploratory nature of this study, no formal sample size estimation was performed. This study will enroll 15 patients and approximately 5 patients will be included in the pharmacokinetic assessment sub-study. The number of patients was chosen based on the clinical experience with other similar proof of concept studies.

## 5. PATIENT CHARACTERISTICS AND STUDY CONDUCT SUMMARIES

### Disposition of Patients

Patient disposition table will be based on all enrolled patients who are consented to participate in the study. The following summaries will be included in the disposition table: total number of patients screened in the study, number of patients who failed screening, number of patients who received treatment, number of patients who completed the study, and number and percentage of patients who discontinued from the study with reason for discontinuation. Percentages will be based on the number of patients who are treated. In addition, the number of patients included in each analysis population (mITT, PP, Safety and PK) will be presented.

### Demographic and Baseline Characteristics

Demographic and baseline characteristics will be summarized based on the mITT, PP and Safety populations.

Descriptive summaries will be provided for the demographic and baseline characteristics. Demographic characteristics such as age, gender, race, ethnicity, height, weight, Body Mass Index (BMI), reproductive status, history of alcohol intake and liver biopsy performed will be summarized and tabulated for all analysis populations. All the continuous variables (i.e., age, height etc.) will be summarized by n, mean, standard deviation, minimum, median and maximum values. All the categorical variables (i.e., gender) will be summarized as counts and percentage.

Document Title:	Statistical Analysis Plan		
Version Number:	1.0	Date:	31 Dec 2021
Protocol Number:	SARO.17.010	Sponsor Name:	Zydus Therapeutics Inc.

### **Medical history, previous and concomitant therapies**

Medical history information will be coded using the Medical Dictionary for Regulatory Activities (MedDRA®, version 21.0). A summary will be provided including the frequency and percentage of patients with medical history terms by system organ class and preferred term for the safety population. A by-patient listing of medical history information will be provided for all enrolled patients including current and past diseases.

Prior therapies are the therapies/medications with stop date prior to first dose of study drug. Any therapy/medication usage at or post first dose of study drug is considered concomitant therapy.

All medications recorded during the study will be coded using the World Health Organization (WHO) Drug Dictionary (version DDEBSEP16). A summary will be provided for the frequency and percent of patients who had previous therapies/medications and a separate summary of patients who had concomitant therapy/medications. Summaries will be based on the safety population and will be by Anatomical Therapeutic Chemical (ATC) classification level 3 term and preferred name.

A listing of all prior and concomitant medications including the reported term, preferred name, ATC level 3 term, start dates, stop dates and other relevant data will be provided for all enrolled patients.

## **6. EFFICACY ANALYSIS STRATEGY**

In this study, efficacy will be evaluated as a secondary objective.

### **6.1 General Considerations**

Categorical variables will be summarized with the frequency and percentage of patients in each category. Continuous variables will be summarized descriptively with the number of patients, mean, standard deviation, minimum, median and maximum values. Change from baseline will be summarized similarly. The change from baseline will be calculated as follows:

$$\text{Change from baseline} = \text{Post baseline value} - \text{Baseline value}$$

$$\text{Percent Change} = (\text{Post baseline value} - \text{Baseline value}) / \text{Baseline value} * 100.$$

The SAS® statistical software (version 9.4) application will be used for all analyses.

Statistical Analysis Plan			
Version Number:	1.0	Date:	31 Dec 2021
Protocol Number:	SARO.17.010	Sponsor Name:	Zydus Therapeutics Inc.

### Decimal Precision

Unless otherwise noted, mean, median, standard deviation, minimum and maximum will be presented to two decimal places, percentage and confidence interval will be presented to one decimal place; and p-values will be presented to four decimal places.

### Missing Date Procedures

Adverse events with completely missing dates will be considered treatment-emergent.

Medications with completely missing end dates will be considered concomitant. Adverse events and medications with partially missing start or end dates will be considered treatment-emergent and concomitant respectively unless the non-missing portion of the dates definitively proves otherwise.

For example, if a patient starts treatment on 20FEB2016, then adverse events with onset dates of FEB2016, 2016, or 05DEC would all be considered treatment-emergent, while onsets dates of 2015 or JAN2016 would not be considered treatment-emergent. Medications starting or ending in FEB2016 or 2016 would be considered concomitant, medications ending in JAN2016 or 2015 would not.

## 6.2 Endpoints

### Efficacy Endpoints

The efficacy endpoints are:

- Changes in hepatic fat as determined by MRI-PDFF and MRE from baseline to Week 24 (EOT visit).
- Changes in metabolic flexibility from baseline to Week 24 (EOT visit).
- Changes in markers of insulin resistance (FSIVGTT, HbA1c and Fructosamine) from baseline to Week 24 (EOT visit).
- Changes in serum liver enzymes (ALT, AST, ALP and Total Bilirubin) from baseline to Week 24 (EOT visit).
- Changes in serum lipid profile (Total cholesterol, Triglycerides, HDL, LDL, VLDL and non-HDL) from baseline to Week 24 (EOT visit).
- Changes in atherogenic lipoprotein which includes sdLDL, LDL size and concentration, subtypes of VLDL and HDL from baseline to Week 24 (EOT visit).
- Change in QoL score from baseline to Week 24 (EOT visit) using SF-36 health survey
- Change in adipose tissue and skeletal muscle volume from baseline to Week 24 (EOT visit) assessed by whole body MRI.

Document Title:	Statistical Analysis Plan		
Version Number:	1.0	Date:	31 Dec 2021
Protocol Number:	SARO.17.010	Sponsor Name:	Zydus Therapeutics Inc.

### Pharmacokinetic Endpoints

The PK parameters for Saroglitazar that may be calculated include the following:

- $C_{max}$ : Peak plasma concentration
- $T_{max}$ : Time to reach peak plasma concentration
- $AUC_{0-t}$ : Area under the plasma concentration vs time curve from time 0 to last measurable concentration
- $AUC_{0-\infty}$ : Area under the plasma concentration vs time curve extrapolated to infinity
- $AUC_{tau}$ : Area under the plasma concentration vs time curve in a 24 hour dosing interval
- $\lambda_z$ : Terminal elimination rate constant
- $t_{\frac{1}{2}}$ : Terminal elimination half-life
- $Vd/F$ : Apparent volume of distribution
- $CL/F$ : Apparent clearance
- $C_{min}$ : Minimal or trough plasma concentration for last dose only
- Accumulation index: Ratio of  $AUC_{tau}$  (last dose)/ $AUC_{tau}$  (first dose)
- Fluctuation index

### 6.3 Efficacy Hypotheses

There are no formal hypotheses testing will be conducted for the efficacy endpoints. The p-values presented for change from baseline are for the descriptive purpose only.

### 6.4 Statistical Methods for Efficacy Analyses

All efficacy endpoints will be summarized descriptively by visit. Descriptive summaries include number of patients, mean, standard deviation, median, minimum and maximum values will be provided for all efficacy endpoints. In addition, 95% confidence intervals will be provided for change from baseline to Week 24 (EOT visit) for all efficacy endpoints. Confidence intervals will be calculated using t-test. Quality of life assessment will be summarized using total scores as well as for each domain.

### 6.5 Sensitivity Analysis

A sensitivity analysis to explore the robustness of the efficacy results with respect to the protocol deviations will be performed using per-protocol population for the efficacy endpoints.

Statistical Analysis Plan			
Version Number:	1.0	Date:	31 Dec 2021
Protocol Number:	SARO.17.010	Sponsor Name:	Zydus Therapeutics Inc.

## 6.6 Subgroup Analyses and Effect of Baseline Factors

Due to the small sample size, no subgroup analysis is planned for this study.

## 6.7 Multiplicity Strategy

Not applicable. No testing of hypothesis will be conducted for this study.

## 6.8 Handling of Missing Data

Clarifications, wherever possible, will be obtained from the respective investigator for any missing data or for any illegible entry, unused or unauthenticated data. Patients are required to have at least one post-baseline assessment to be included in the mITT population. Last Observation Carried Forward (LOCF) will be used for the imputation of post-baseline missing values. Baseline values will not be carried forward for the imputation of missing values.

## 7. ANALYSIS OF PHARMACOKINETIC ENDPOINTS

Pharmacokinetic analyses will be performed using the PK population.

Blood samples for pharmacokinetic analysis will be collected on Day 1 and Week 24 visit at Pre-dose (0.0), 0.5, 1.0, 2, 3, 4, 6, 8, 10 and 24 hour post-dose. In addition, pre-dose sample will be collected at Week 4, 8, 12, 16 and 20 visits.

The PK endpoints will be derived from the plasma concentration-time data for Saroglitazar for each patient, provided that there are sufficient data available to estimate each PK parameter. The AUC values will be calculated using the linear trapezoidal method. Actual sampling times of individual patient will be used in the PK analysis.

Descriptive summaries for plasma concentration (n, arithmetic mean, standard deviation, median, minimum, maximum, geometric mean, and coefficient of variation) will be presented by sample collection time points. For calculating descriptive statistics for plasma concentrations, all post-dose plasma concentrations below the limit of quantification (BLQ) will be replaced by one half the lower limit of quantification (LLOQ). All pre-dose plasma concentrations below the limit of quantification (BLQ) will be replaced by zero. Plasma concentrations will be reported with three significant figures.

For the determination of PK parameters, actual collection times will be used as opposed to scheduled collection times.

Document Title:	Statistical Analysis Plan		
Version Number:	1.0	Date:	31 Dec 2021
Protocol Number:	SARO.17.010	Sponsor Name:	Zydus Therapeutics Inc.

Line plots (Linear and semi-log) of the mean concentration versus time curves will be plotted using scheduled times. Individual patient graphs will also be presented using actual times.

Descriptive statistics (number of patients, arithmetic mean, standard deviation, median, minimum, maximum, geometric mean, and coefficient of variation) will be used to summarize the estimated pharmacokinetic parameters. All plasma-concentration data and PK parameter values will be provided in listings.

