#### 5.2 DOSAGE AND TREATMENT SCHEDULE

Saroglitazar magnesium 4 mg will be given once daily orally in the morning 60 minutes before breakfast without food, for 24 weeks. However, on the day of the scheduled clinical visit, subjects will have the IP administered on site after fasting blood sample collection. If on the

Approved by:	Protocol No.: SARO.17.010
[name] [name]	Version No.: 7.0

CONFIDENTIAL

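### The SAP sets every pre-dose BLQ concentration to zero, including on-treatment troughs, so one BLQ trough makes that visit's planned geometric mean 0 or undefined.

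*SAP*

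**What the plan says.** SAP section 7 gives two substitution rules for descriptive statistics of plasma concentration. For samples before a dose: "All pre-dose plasma concentrations below the limit of quantification (BLQ) will be replaced by zero". For samples after a dose: "all post-dose plasma concentrations below the limit of quantification (BLQ) will be replaced by one half the lower limit of quantification (LLOQ"). The first rule is not restricted to Day 1.

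The section uses the term pre-dose for on-treatment samples as well. Besides the 0.0 h sample of the full profiles on Day 1 and at Week 24, it says: "In addition, pre-dose sample will be collected at Week 4, 8, 12, 16 and 20 visits". Protocol section 5.2 says that on clinic days "subjects will have the IP administered on site after fasting blood sample collection", so these later samples follow the previous day's dose and precede that day's dose.

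The planned concentration summary includes the "geometric mean, and coefficient of variation) will be presented by sample collection time points". Nothing in the SAP says how zeros enter the geometric mean. SAP section 4 puts about 5 patients in the pharmacokinetic sub-study.

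**The concern.** Before the first dose the patient has had no study drug, so zero is the natural value for a BLQ result. At Weeks 4 to 24 the patient is on daily treatment, and a BLQ result says only that the concentration is below the LLOQ. Zero is then the extreme low end of what is possible, and it is the one value that a geometric mean cannot absorb.

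There is also an inconsistency at Week 24. The pre-dose sample and the 24 h post-dose sample are at the same nominal time after a dose. If BLQ, the first becomes 0 and the second LLOQ/2, so two comparable troughs would be summarised on different bases.

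Pharmacokinetics is a secondary objective. Protocol section 6.2.8 derives the parameters for the first and last dose, with Cmin for the last dose only. For Weeks 4 to 20 the summary by time point is therefore the only numerical summary specified, apart from listings and plots.

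**Working it through.** **Inputs from the documents.** BLQ pre-dose becomes 0, BLQ post-dose becomes LLOQ/2, and a geometric mean (GM) is reported at each time point (SAP section 7); about 5 patients (SAP section 4). Neither document gives an LLOQ, a half-life or an expected trough, so there is no planned figure to reproduce. All concentrations below are assumptions, in LLOQ units.

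**Algebra.** GM = (x1 × … × xn)^(1/n) = exp(mean of ln x). One zero makes the product 0 and the mean of logs minus infinity. This needs no assumption about the drug. Software returns 0, returns missing, or drops the zero and uses the other n − 1 values.

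**Illustration: n = 5, four troughs at 2 and one BLQ.**

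| Handling | Arithmetic mean | SD | CV | Minimum | GM |
|---|---|---|---|---|---|
| Zero, as written | 8/5 = 1.60 | √(3.2/4) = 0.89 | 56% | 0 | 0, or 2.00 if the zero is dropped |
| LLOQ/2 | 8.5/5 = 1.70 | √(1.8/4) = 0.67 | 39% | 0.5 | (2⁴ × 0.5)^(1/5) = 1.52 |

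The median (2), maximum (2) and n (5) are the same in both rows.

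**Other levels of the four detectable troughs.** With the four at m and an undetected true value c, the true GM is (m⁴ × c)^(1/5). Taking c from 0.1 to 1.0:

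| m | True GM, c = 0.1 to 1.0 | Zero rule | Zero dropped | LLOQ/2 |
|---|---|---|---|---|
| 2 | 1.10 to 1.74 | 0 | 2.00 | 1.52 |
| 5 | 2.29 to 3.62 | 0 | 5.00 | 3.15 |
| 10 | 3.98 to 6.31 | 0 | 10.00 | 5.49 |

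The arithmetic mean differs between the two rules by 0.5/5 = 0.10 at every m.

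**Unequal troughs.** With 2, 3, 4, 5 and 6, the GM is 720^(1/5) = 3.73. If the lowest is BLQ instead, the GM is 0 as written, 360^(1/4) = 4.36 if the zero is dropped, and (0.5 × 360)^(1/5) = 2.83 with LLOQ/2. Dropping the zero raises the GM when a patient's exposure has fallen.

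**Sensitivity to n only.** If each patient has chance p of a BLQ trough, independently, at least one of 5 is BLQ at a visit with probability 1 − (1 − p)⁵: 9.6% at p = 2%, 22.6% at 5% and 41.0% at 10%. These rates are assumed and say nothing about this drug.

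**Day 1 pre-dose.** All values are expected to be BLQ and so zero. The planned GM is then 0 or undefined and the CV is 0/0. This is harmless, but the tables need a stated convention.

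**The case against.** The main objection is that, Day 1 aside, nothing goes wrong unless an on-treatment trough is BLQ, and the documents do not show how likely that is. This stands.

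The consequence is also small. The rule is worded for descriptive statistics of concentrations, visit-level trough means are not among the listed PK endpoints, all individual values are listed, and a GM of 0 is a visible oddity. This stands too, though a silently dropped zero would be less visible.

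The range comparison is weaker than it looks. LLOQ/2 falls inside the true range by construction, since 0.5 lies between 0.1 and 1.0, and the cut at 0.1 is arbitrary: as the true value approaches 0, so does the true GM. LLOQ/2 is not shown to be accurate. At m = 2 it is 38% high when c = 0.1 (1.52 against 1.10) and 13% low when c = 1.0 (1.52 against 1.74). At c = 1.0 the dropped-zero value is out by the same ratio, 15% high (2.00 against 1.74). The case for LLOQ/2 is therefore consistency with the SAP's own post-dose rule and a computable GM, not accuracy.

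Three other passages could be raised. Protocol section 8.2.6 says concentrations will not be imputed, but the SAP introduction says that the SAP's differences supersede the protocol. Protocol section 5.2 allows blood to be drawn from a patient who twice arrives already dosed, so an occasional sample may not be a true trough; that is an exception. Protocol section 6.2.8 refers to a separate PK manual, not available here, but the SAP's rule is explicit.

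A single sentence omitting the GM wherever a zero occurs would remove the misleading 0. It would leave the Week 24 inconsistency, and it would lose the GM at any visit with a BLQ trough.

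**Conclusion.** The concern holds, as a minor point. Followed as written, the rule gives a GM of 0 or undefined at any visit with a BLQ trough, and it treats the two nominally equivalent Week 24 troughs differently. Both follow from the SAP text and algebra alone. The sizes in the illustration rest on assumed concentrations, and the frequency of BLQ troughs is unknown. The damage is limited to the descriptive concentration summaries: the GM above all, with the SD, CV and minimum also affected. No effect on AUC, Cmin or the accumulation index has been shown.

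**What to change.** In SAP section 7:

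- Limit the zero rule to the Day 1 sample taken before the first dose.
- Apply the existing LLOQ/2 rule to all later samples, including the pre-dose samples at Weeks 4, 8, 12, 16, 20 and 24.
- Report the number of BLQ values at each time point.
- State that the geometric mean is not calculated where zeros are present, which would then be Day 1 pre-dose only.

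The cost is two or three sentences of SAP wording and no extra data. LLOQ/2 remains a convention; the BLQ counts let the reader see how much each summary depends on it.
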